In this six month In- Vivo single blinded Randomized Clinical Study, a total number of 50 patients with complain of dentine hypersensitivity will be selected in two groups after taking consent. Group A and B will receive Propolis and Dentine Bonding Agent respectively by a trained operator. Recordings of Dentin Hypersensitivity will be obtained at Day 0, before and after the application of experimental agents, and also on Day 7, 15 and 30 by the Researcher. Response will be measured by Visual Analog Scale and Schiff Cold Air Sensitivity Scale. SPSS v.20 will used to analyze the data with level of significance set at $p < 0.05$. Friedman test will be applied to see the comparison within groups and Wilcoxon Signed Rank test will be used for Pairwise comparison. Mann Whitney U-Test will be applied for comparison between groups.

Key Words: Dentin Hypersensitivity, Propolis, Dentine Bonding Agent, Visual Analog Scale (VAS), Randomized Clinical Trail, Schiff Cold Air Sensitivity Scale

CHAPTER 1: INTRODUCTION

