1.6 Null Hypothesis

[figure not shown]
There is no difference in the efficacy of Propolis and Dentine Bonding Agent in the treatment of Dentin Hypersensitivity

1.7 Operational Definitions:

Dentine Hypersensitivity: Painful condition that arises from exposed vital dentine due to external stimulation of exposed dentinal tubules. ^{1,2}

Scaling and root debridement [SRD]: Scaling refers to the removal of plaque and calculus from the tooth surface whereas debridement is the removal of the necrotic cementum from the root surface.

Visual Analog Scale [VAS]: A Visual Analogue Scale (VAS) is a measurement instrument for subjective characteristics or attitudes that cannot be directly measured. This psychometric response scale is frequently used in epidemiologic and clinical research to measure the intensity or frequency of various symptoms.

Schiff cold air sensitivity scale⁴⁹: This scale is mainly used to evaluate subject response to a stimulus like air or evaporative. This scale is scored as follows:

1. Subject does not respond to air stimulus.
2. Subject responds to air stimulus but does not request discontinuation of stimulus.
3. Subject responds to air stimulus and requests discontinuation or moves from stimulus.
4. Subject responds to air stimulus, considers stimulus to be painful, and requests discontinuation of the stimulus.

CHAPTER 2: METHODOLOGY

2.1 Study Design:

A Single blinded Randomized Clinical Trial.

2.2 Study Setting:

This singled- centered Study will be conducted in Periodontology Department of Dow International Dental College (DIDC) of Dow University of Health Sciences (DUHS).

2.3 Study Duration:

Study will be conducted in six months after approval of the synopsis

2.4 Study Population:

2.4.1 Inclusion Criteria:

1. Subjects included in this study will be selected from outpatients attending the periodontology department of DIDC for the problem of Dentin Hypersensitivity.
2. Healthy males or females of 20- 45 years of age and will have at least 2 vital teeth with hypersensitivity on facial surfaces to evaporative stimulus.
3. Patients with Miller's Class I and II gingival recession will be included.
4. Patients with Score I of Silness and Loe Plaque Index⁵⁰.
5. The patients should have no systemic and mental illness.
6. Patients who used Flouride dentifrices for hypersensitivity but could not get relief from it.

2.4.2 Exclusion Criteria:

[figure not shown]

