1. Patients with Carious, Cracked or Restored teeth, Abutment teeth used of Removable or Fixed Prosthesis and tooth with any other dental pathology.
2. Patients using analgesics, mood alteration drugs during last six months.
3. Smoker, pregnant and nursing mothers.
4. Patients using tooth whitening or bleaching agents in the last six months,
5. Patients undergoing orthodontic therapy and history of periodontal surgery during last six months.
6. Patients who refuse to give consent.
7. Patients who had Score 2 and 3 of Calculus index will also be excluded from this study.

2.5 Sample Size:

Total 50 patients will be carried out (25 in each group). Using PASS version 11, test for Pair means with 99% Confidence Interval and Power of test, mean difference of degree of sensitivity 1.8 (1.9 – 0.01) ²⁷ and 0.42 of Standard Deviation difference (3.35 – 2.93) ²⁷, sample size is 5 patients per group which we have increased to 25 patients per group.

2.6 Sampling Technique:

Diagnosis of Dentine Hypersensitivity will be made by obtaining detailed dental history and clinical examination of the patients prior to include in the study. History and clinical examination will eliminate and exclude the other forms and causes of Dentine Hypersensitivity which will not meet the inclusion criteria of this study. Definitive diagnosis of Dentine Hypersensitivity will be made by using Evaporative or Air blast stimulus from triple dental syringe on the sensitive surface. Then participants will be allocated to two groups through sealed envelope method. Groups will be named as Group A (Propolis) and Group B (Dentine Bonding Agent). It will only be disclosed out at the time of application of desensitizing agents by Operator.

2.7 Data Collection Procedure:

After explanation of the procedure, efficacy and safety of the materials used, possibilities of receiving either treatment options that is Propolis or Dentine Bonding Agent, the patients will be asked to sign a consent form at first (Appendix I & II). After the consent, a complete history will be obtained from the patient regarding his systemic health, medications, dental treatment and hygiene habits and smoking (Appendix III).

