At baseline (Day 0), thorough oral prophylaxis will be done for all the patients which include Scaling & Root Debridement with Polishing and detailed oral hygiene instructions should be given. Scaling is recommended to remove plaque, calculus and food remnants so clean tooth surface will be available for application of Propolis and Dentine Bonding Agent. Subjects will be provided with kit containing same type of standard Toothpaste (Colgate[®] Maximum Cavity protection PLUS Sugar Acid Neutralizer[™]) and Toothbrush (Colgate[®] 360[°] Sensitive Pro-Relief[™]) for oral hygiene during research time. Proper tooth brushing technique will be explained and demonstrated to each and every patient. Dietary counseling will also be done in order to avoid intake of excessive acids during study period.

After debridement, pretreatment assessment will be done by trained examiner. To evaluate and assess Dentin Hypersensitivity, Evaporative stimulus (controlled air blast stimulus) will be used from dental triple syringe or air water syringe which will be directed onto the affected area from a distance of 10mm for up to two seconds with complete isolation of the adjacent teeth by cotton roll. Responses will be measured on 10 cm line on Visual Analog Scale (VAS)⁵² which will be scored as 0 (No Pain), 1-3 (Mild Pain), 4-6 (Moderate Pain) and 7-10 (Severe Pain). Another scale names Schiff Cold Air Sensitivity Scale⁴⁹ will be used to measure response graded as 0, 1,

2, 3. Responses from all patients will be recorded by a single examiner, who will be blind to the applied desensitizing agents.

The patients will be allocated in to two respected groups, according to randomization by the process of sealed envelopes. The groups will be divided according to the desensitizing agents. Group A includes patients that will receive Propolis as a treating agent. Propolis obtained from Margalla hills, Islamabad by NARC (National Agriculture Research Council, Islamabad). Plant source origin is *Acacia modesta* and *Apis mellifera* bees collect it. The 30% ethanolic extract of Propolis from raw Propolis will be obtained in Pakistan Council of Scientific & Industrial Research (PCSIR) by dissolving the Propolis in 95% Ethanol and straining out the precipitate. Group B includes patients that will receive Dentine Bonding Agent (Scotchbond™ Universal Adhesive, 3M ESPE Dental Products, St. Paul, MN, USA).

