Only the Principal Investigator will be blind to the intervention given to the participants. Application of desensitizing agents to participants will be carried out by trained and experienced operator and it will only be disclosed to operator at the time of application. Operator will inform the participant about the intervention before applying and patients will not be blinded. Desensitizing agents will be applied on day 0 (baseline). Complete isolation of proximal sides from hypersensitive teeth will be done by using cotton rolls. Hypersensitive teeth surfaces will be dried by cotton pellets. Propolis will then be applied by brush on sensitive surfaces and left undisturbed for 60 seconds to let it dry. Application of Dentine Bonding Agent on sensitive surfaces will be applied single coated for 20 seconds, gently apply air for 5 seconds and cure for 10 seconds (as manufacturer's instructions). For Score 4-6 s(Moderate Pain) & 7-10 (Severe Pain) on VAS and grade 3 (Subject responds to air stimulus, considers stimulus to be painful and requests discontinuation of stimulus) of Schiff Cold Air Sensitivity Scale, application of Propolis

and Dentine Bonding Agent will be applied under Local Anesthesia and response will be recorded on next day.

Care should be taken to ensure that none of the products will touch other areas of oral mucosa. Patients will be instructed not to rinse, drink or eat for half an hour after the application of treatment agents and avoid using any desensitizing dentifrices during the course of investigation.

The clinical evaluation of Dentin Hypersensitivity will be done before and after the application of Desensitizing agents at baseline (Day 0), and also on day of re-assessment at 7th, 15th and 30th day (Appendix III).

2.8 Data Analysis:

2.8.1 Study Variables:

Independent Variables:

- Sessions (Days)
- Groups

Dependent Variables:

- Visual Analog Scale (VAS)
- Schiff Cold Air Sensitivity Scale

2.8.2 Statistical Analyses:

Statistical Package for Social Sciences (SPSS) version 20 will be used to analyze the data. The level of statically significance will be set at $p < 0.05$. to see the comparison within groups, Friedman test will be applied. For Pairwise comparison, Wilcoxon Signed Ranked Test will be used. For between groups comparison, Mann- Whitney U- Test will be applied.

2.9 Ethical considerations:

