APPENDIX-II

[figure not shown]
Date: _____ Form no: _____ Envelop: _____

Patients Name: _____ Age: _____ Sex: _____

Address: _____

Contact No. : _____ Occupation: _____

VAS

Schiff Cold Air Sensitivity Scale

0 = Subject does not respond to air stimulus

1 = Subject responds to air stimulus but does not request discontinuation of stimulus

2 = Subject responds to air stimulus and requests discontinuation or moves from stimulus

3 = Subject responds to air stimulus, considers stimulus to be painful and requests discontinuation of stimulus

	VAS	SCASS
Day 0 (Before Application)		
Day 0(Immediately after application)		
Day 7		
Day 15		
Day 30

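### The between-group comparison ignores the Day 0 pre-application scores; adjusting for them would add precision with no new data

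*Combined protocol and SAP*

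**What the plan says.** Section 2.8.2 states: "For between groups comparison, Mann- Whitney U- Test will be applied". The Abstract agrees: "Mann Whitney U-Test will be applied for comparison between groups". The remaining tests are for comparisons over time: "to see the comparison within groups, Friedman test will be applied. For Pairwise comparison, Wilcoxon Signed Ranked Test will be used". Section 2.8.1 lists only session and group as independent variables. No ANCOVA, regression, stratified test or other baseline adjustment appears anywhere. The plan does not say whether Mann-Whitney is applied to scores or to change from baseline, nor at which visit. Scores are the apparent reading.

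The baseline is already measured. Section 2.7 says "After debridement, pretreatment assessment will be done by trained examiner" and "The clinical evaluation of Dentin Hypersensitivity will be done before and after the application of Desensitizing agents at baseline (Day 0". The data form in Appendix II has a row "Day 0 (Before Application" with a VAS cell and a Schiff cell. Sections 2.6 and 2.7 say the agent is disclosed only at application, so this score cannot have been affected by treatment.

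**The concern.** Section 2.4.1 requires "at least 2 vital teeth with hypersensitivity on facial surfaces to evaporative stimulus" but sets no minimum score. Section 2.7 grades VAS as mild, moderate or severe and makes separate provision for the higher scores. Baseline severity can therefore differ between patients. If it predicts later severity, a test that ignores it leaves explainable variation in the error term. With only 25 per group, that means a wider interval and lower power than the same data could give. A chance baseline imbalance also passes into the estimated difference in proportion to r.

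**Working it through.** **The plan's own figure.** Section 2.5 arrives at 5 per group. A two-sided paired t-test with difference 1.8, SD 0.42, alpha 0.01 and power 0.99 (99% read as applying to both confidence and power) does give n = 5, with actual power 99.5%. However, the 0.42 is "0.42 of Standard Deviation difference (3.35 – 2.93", a difference between two SDs. It cannot serve as the SD of the outcome, so the two SDs are used here instead.

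**Inputs.**
- From section 2.5: n = 25 per group, difference 1.8, SDs 3.35 and 2.93. The section does not say which measurement these figures describe, and it uses the 1.8 in a paired calculation. Treating it as a between-group VAS difference is an assumption.
- From section 2.8.2: significance level 0.05, taken as two-sided.
- Assumed: r = 0.3, 0.5, 0.7, and SDs of 2.6 and 2.0 as alternatives.

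**Formulas.**
- Pooled SD = √((3.35² + 2.93²)/2) = 3.147.
- ANCOVA residual SD = SD × √(1 − r²), with 47 df instead of 48.
- The variance factors 1 − r² are 0.91, 0.75 and 0.51. These are worth 25/0.91 = 27, 25/0.75 = 33 and 25/0.51 = 49 unadjusted patients per group.
- Noncentrality = 1.8 / (residual SD × √(2/25)). At SD 3.147 unadjusted, this is 1.8/(3.147 × 0.283) = 2.02.

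**Power by noncentral t, normal data.**

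| SD | Unadjusted | r = 0.3 | r = 0.5 | r = 0.7 |
|---|---|---|---|---|
| 3.15 | 51% | 55% | 63% | 79% |
| 2.6 | 67% | 71% | 79% | 92% |
| 2.0 | 88% | 90% | 95% | 99% |

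**95% CI half-width at SD 3.15** = t × residual SD × √(2/25): 1.79 unadjusted, then 1.71, 1.55 and 1.28.

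**Chance imbalance.** P(baseline difference of 0.5 SD or more) = 2 × (1 − Φ(0.5/√(2/25))) = 0.077, about 8% of trials. The resulting shift in the unadjusted difference is r × 0.5 × SD. At SD 3.147 this is 0.47, 0.79 or 1.10 points; at SD 2.0 it is 0.3, 0.5 or 0.7.

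**Comparison with the planned test.** The table above has an unadjusted t-test as comparator, so Mann-Whitney itself was simulated (8,000 trials per setting). The latent data were bivariate normal with SD 3.147. Baseline mean was 6, limited to 1–10; follow-up mean was 4, limited to 0–10. Scores were rounded. The latent difference was 1.8 (1.57 as observed).

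| Analysis | r = 0.3 | r = 0.5 | r = 0.7 |
|---|---|---|---|
| Mann-Whitney, scores | 48% | 49% | 48% |
| Mann-Whitney, change | 36% | 48% | 66% |
| ANCOVA | 52% | 59% | 74% |
| Rank ANCOVA (Quade) | 51% | 58% | 72% |

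Under no treatment difference, all four rejected in 4.2–5.0% of trials.

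**The case against.** The planned test is valid, and a rank method is a defensible choice for a four-grade scale and a bounded VAS. That stands, and it makes this an efficiency point only.

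The size of the gain rests on figures the documents do not give. That also stands. No r is stated, and the baseline is taken after same-day debridement, which could weaken it. The powers are illustrations, not properties of this trial.

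If Mann-Whitney is meant for change scores, baseline is already partly used. In the simulation ANCOVA was still ahead of that reading, by 52 − 36 = 16, 59 − 48 = 11 and 74 − 66 = 8 points.

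The strongest objection is a floor effect. Sections 1.2 and 1.3 expect both agents to work, so many follow-up scores may be zero. With a latent follow-up mean of 1 in the worse arm and about 55% zeros, power at r = 0.3, 0.5, 0.7 was 42/39/40% for Mann-Whitney on scores, 41/43/53% for ANCOVA and 44/46/57% for rank ANCOVA. In that setting linear ANCOVA gains nothing at r = 0.3 and trails rank ANCOVA throughout; at r = 0 it loses about 2 points (40% to 38%). So linear ANCOVA is not always ahead, and its cost is not exactly zero. Adjustment in rank form still holds up.

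Two further points stand. Chance imbalance is already contained in the unadjusted standard error, so it is another view of the same lost precision and not an additional harm. And no gain has been quantified for Schiff, where four grades and 25 per group may give sparse cells.

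**Conclusion.** The point holds as an improvement in efficiency, not as a correction of an error. On normal data at SD 3.15, adjustment raises power for a difference of 1.8 from 51% to between 55% and 79% for r from 0.3 to 0.7. On rounded, bounded VAS, the gain of ANCOVA over Mann-Whitney on scores runs from about 4 points at r = 0.3 to about 26 at r = 0.7 (74 − 48). It is smaller if the SD is well below 3.15, because unadjusted power is then already high. It is also smaller if many follow-up scores are zero. The downside is slight: one degree of freedom, which at r = 0 takes normal-theory power from 50.9% to 50.8%, and about 2 points in the heavy-floor case. All of this assumes a two-sided 5% test, no dropout, and that the section 2.5 figures apply to the VAS. Baseline adjustment is not the only source of precision, since the Day 7 and Day 15 scores could also be used.

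**What to change.** Add a short paragraph to section 2.8.2, fixed before any data are seen:

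- Name one visit for the main between-group comparison (Day 30, for example; the plan names none).
- For VAS, fit ANCOVA on group and baseline VAS, and report the adjusted mean difference with its 95% CI.
- Report rank ANCOVA (Quade), and Mann-Whitney with a Hodges-Lehmann estimate, as fixed sensitivity analyses, with no switching on the basis of residuals. If many zero scores are expected, rank ANCOVA could be made the main analysis, provided that is decided now.
- For Schiff, fit a proportional-odds model with group and baseline grade, and state in advance how sparse grades will be handled.
- Define the covariate as the Day 0 score before application. The Day 0 score immediately after application is a post-treatment measure and must not be used.
- Patients have two or more sensitive teeth but the form has one cell per scale per visit, so state how the patient-level score is formed, identically at baseline and follow-up.

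The data are already collected and SPSS can fit these models. No patients, visits or measurements are added.

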1.5 Objectives

The objective of this study is to explore which is more effective between Propolis and Seventh generation Dentine Bonding Agent for the treatment of Dentine Hypersensitivity.

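### Section 2.8.2 plans only significance tests between Propolis and Dentine Bonding Agent, with no effect estimate or confidence interval, so no result can be sized and a non-significant one cannot be told apart from an inconclusive one.

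*Combined protocol and SAP*

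**What the plan says.** Section 2.8.2 is the whole analysis plan. It names SPSS version 20, a significance level of p < 0.05, the Friedman test within groups and the Wilcoxon signed-rank test for pairwise comparisons. For the two agents it adds: "For between groups comparison, Mann- Whitney U- Test will be applied". The abstract repeats the same list.

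Neither place names a between-group estimate or an interval. The only confidence interval in the document is the 99% one in the sample-size sentence of section 2.5, where it is an input to the calculation and not a planned result.

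Section 1.5 states the aim: "The objective of this study is to explore which is more effective between Propolis and Seventh generation Dentine Bonding Agent". Section 1.6 gives the only hypothesis: "There is no difference in the efficacy of Propolis and Dentine Bonding Agent in the treatment of Dentin Hypersensitivity". There is no statement of how a non-significant result will be reported.

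**The concern.** The objective asks which agent works better, and the rationale in section 1.3 promises to identify the better of the two options. A p-value alone answers only part of that. If p < 0.05, the reader learns the direction of the difference but not whether it is 0.5 or 3 points on a 10 cm scale, and so cannot judge whether it matters to patients.

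If p >= 0.05, the reader cannot tell whether the agents perform alike or whether 50 patients were too few to show a difference. Section 1.2 reports that both agents reduce sensitivity, so a non-significant comparison is a realistic outcome. It would stand beside a null hypothesis of no difference, with nothing in the planned output to show how large a difference remains possible.

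**Working it through.** **Inputs**

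- Group size: 25 per group (section 2.5).
- Planning difference: 1.8 (section 2.5, "mean difference of degree of sensitivity 1.8 (1.9 – 0.01"). The subtraction as printed gives 1.89. I use 1.8, the figure the plan carries forward.
- SDs: 3.35 and 2.93 are printed in section 2.5 ("0.42 of Standard Deviation difference (3.35 – 2.93"). The scale, group and time point are not given. I treat them as one possible pair of per-group SDs and add common SDs of 2.5 and 2.0 as assumptions.
- Significance level: 0.05 (section 2.8.2). Sidedness is not stated. I assume two-sided, because the objective allows either agent to be better.
- Dropout: none assumed, which favours the plan.

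**Step 1. The plan's own figure.** Section 2.5 uses a "test for Pair means with 99% Confidence Interval and Power of test" and concludes that "sample size is 5 patients per group which we have increased to 25 patients per group". A paired t-test with difference 1.8, SD 0.42, two-sided alpha 0.01 and power 0.99 gives n = 5 (power 0.995 at n = 5, 0.893 at n = 4), so the 5 is reproduced. The 0.42 is one SD minus another (3.35 − 2.93). That is not the SD of an outcome or of a paired difference, so it cannot show how precise the comparison between agents will be.

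**Step 2. Precision of the difference with 25 per group.** SE = sqrt((s1² + s2²)/25), and the 95% half-width = t(48, 0.975) × SE, with t = 2.011.

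- SDs 3.35 and 2.93: SE = sqrt((11.22 + 8.58)/25) = 0.890; half-width 2.011 × 0.890 = 1.79.
- SD 2.5: SE = sqrt(12.5/25) = 0.707; half-width 1.42.
- SD 2.0: SE = sqrt(8/25) = 0.566; half-width 1.14.

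Simulated Hodges-Lehmann intervals are slightly wider, with mean half-widths of 1.84, about 1.45 and 1.16.

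**Step 3. Chance of p >= 0.05 when the true difference is 1.8.** Simulated Mann-Whitney tests on normal data, 25 per group, one test:

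| SDs | p >= 0.05, Mann-Whitney | p >= 0.05, t-test |
|---|---|---|
| 3.35 and 2.93 | 52% | 49% |
| 2.5 | 33% | 30% |
| 2.0 | 15% | 12% |

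**Step 4. What this means for reading the result.** With the printed SDs, an observed difference of zero would carry an interval of about −1.8 to +1.8, so it would barely rule out, or not rule out, the plan's own planning difference. With an SD of 2.0 the interval would be about −1.2 to +1.2, which excludes 1.8 but not differences of a point. The test reports the same p-value in both cases. Only the interval separates them.

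**The case against.** **The plan does not forbid estimates.** Section 2.8.2 is a few sentences in a thesis proposal, and medians or intervals could be added at write-up from the same data. That is true and limits the seriousness of the point. But an estimate chosen after the results are known is weaker than one named beforehand, and the plan as it stands names none.

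**A reader might infer that the plan commits the author to declaring equal efficacy when p >= 0.05.** The documents do not support that. Section 1.6 is an ordinary null hypothesis, section 1.5 asks a superiority-type question, and no section states a rule for accepting the null or proposes an equivalence claim. For the same reason an equivalence margin is not needed.

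**A reader might infer that the trial has an even chance of missing a difference of 1.8.** That is also too strong, for two reasons.

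- The 52% depends on SDs that section 2.5 does not identify. The printed figures do not fit together as VAS scores: on a 0 to 10 scale a mean of 0.01 allows an SD of at most sqrt(0.01 × 9.99) = 0.32, so an SD near 3 cannot belong to a group with that mean. If 1.9 and 0.01 are something else, such as changes, the SDs may not be those of the scores to be compared.
- The figure is for one test. The plan has two scales and four post-treatment readings, with no primary comparison named. Suppose the printed SDs apply, the 1.8 difference is constant, and readings correlate at 0.5 to 0.9 (assumed). Then at least one of four VAS tests is significant in roughly 80% down to 63% of simulated trials. That raises a separate multiplicity question. It does not supply an effect size.

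The absence of an estimate and interval does not depend on any SD, so that part is untouched.

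**Conclusion.** The point holds as a gap in the planned analysis. Followed as written, section 2.8.2 gives no size for the difference between the agents and nothing to separate an inconclusive result from a reassuring one.

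The size is conditional: for a single two-sided Mann-Whitney test with 25 per group and a true difference of 1.8, the chance of p >= 0.05 is roughly 15% to 52%, and the 95% half-width about 1.2 to 1.8. The lower end assumes an SD of 2.0. The upper end takes the printed 3.35 and 2.93 as per-group SDs, which the plan does not establish. Both assume roughly normal data and no dropout. The trial can run as designed; what should change is how its main comparison is reported.

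**What to change.** Keep the Mann-Whitney test in section 2.8.2 and add, wherever it is used between groups:

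- For VAS, the Hodges-Lehmann difference (Propolis minus Dentine Bonding Agent) with its 95% confidence interval.
- For the Schiff scale, the probability that a Propolis patient has a lower grade than a Dentine Bonding Agent patient, with its 95% confidence interval. This is U / (n1 × n2), where U counts the pairs in which the Propolis patient has the lower grade and ties count one half. With full data n1 × n2 = 25 × 25 = 625 pairs.
- A sentence stating that p >= 0.05 will be reported as no difference shown, together with the interval, and not as equal efficacy.

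The cost is one short paragraph and slightly more analysis work. No extra patients, visits or measurements are needed. The downside is that a null result has to be worded more cautiously.
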